7 INVESTIGATIONAL PLAN

7.1 Overall Design and Plan of the Study

This is an open-label, multicenter Phase 2 study of CDX-3379 in combination with cetuximab in patients with cetuximab-resistant HNSCC. Patients will be treated with CDX-3379 plus cetuximab until progressive disease, unacceptable toxicity, or other criteria for discontinuation of study treatment (Section 7.4.1) are met.

The study was initially designed according to a Simon's 2-stage design in which one tumor response (CR or PR) would need to be observed in the first 13 evaluable patients before completion of accrual to a total of 27 evaluable patients. Patients who discontinue treatment in the absence of progression/symptomatic deterioration/death before the first tumor assessment will be considered unevaluable for primary analysis and will be replaced. Following completion of stage 1 of the study, where 1 complete response was observed, emerging biomarker data were reviewed to assess correlation with efficacy. In the overall CDX-3379 development program, in a small patient dataset, FAT1 and NOTCH1, NOTCH2 and NOTCH3 mutations appeared to be associated with clinical activity including objective response and durable stable disease. Given these findings, the study design has been amended to enroll up to approximately 45 total patients, including at least 15 patients whose tumor harbor a FAT1 mutation based on retrospective gene sequencing. Screening tissue samples will be required to be submitted as directed by the Sponsor at the time of enrollment to allow for gene sequencing and tracking the number of patients whose tumor harbor a FAT1 mutation.

Tumor assessments will be performed approximately every 6 weeks during treatment. Patients who discontinue treatment in the absence of progression will continue to have assessments approximately every 12 weeks until documented progression or initiation of alternate anticancer therapies. Tumor response will be assessed by the investigator in accordance with RECIST 1.1 guidelines (Eisenhauer, et al. 2009) (Section 10.2.1 and Appendix 2).

Continuous evaluation of toxicity will be performed by the investigators and Celldex throughout the entire course of patient treatment and through 30 days following the last dose of CDX-3379. Subsequently, patients will be followed for survival, with contact every 12 weeks until study closure.

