4.2. Presentation of results

Descriptive statistics will summarize results. Unless otherwise stated, confidence intervals (CIs) will be computed using a two-sided $\alpha=0.05$ level of significance.

Standard descriptive statistics, such as mean, standard deviation, median, quartiles, minimum, and maximum, will be calculated for continuous variables. For discrete variables, descriptive analyses will be based on numbers of patients and related percentages of patients with non-missing data. Unless otherwise specified, tables and figures will present such descriptive statistics for both the observed values and change at each scheduled visit.

Medical history and AEs will be coded using Medical Dictionary for Regulatory Activities (MedDRA®). Prior and concomitant medications will be coded using World Health Organization Drug (WHO) Global dictionary.

In addition to tabular summaries, by-patient listings will present all relevant electronic case report form (eCRF) data.

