4.9. Sample size determination and power calculation

The original sample size for the study was based on Simon's 2-stage MinMax design. The first stage was completed, and the futility stopping rule was not met. Protocol Amendment 1 increased the total sample size from 30 to approximately 45 treated patients, including at least 15 patients whose tumors harbor a FAT1 mutation based on retrospective gene sequencing.

According to the protocol, the planned sample size of 45 treated patients provides >80% power to rule out <20% ORR based on the lower 95% confidence bound for the for different underlying true response rates if the true response rate is $\geq 40\%$.

The cohort size of 15 treated patients in the FAT1 mutation-positive cohort provides nearly 80% power to rule out <15% ORR if the true response rate is $\geq 40\%$.

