6.2. Secondary efficacy endpoints

6.2.1. Duration of response

DOR is defined as the interval from which measurement criteria are first met for CR or PR until the first date that progressive disease is objectively documented or death, whichever occurs first. Patients who have not progressed or died will be censored on the date of last evaluable tumor assessment; patients who did not have any on-study assessments and have not died will be censored on the date of first dose. If a patient receives subsequent anti-cancer treatment before documented progression, then DOR will be censored on the last evaluable tumor assessment on or before initiation of subsequent anti-cancer treatment. The censoring rules are outlined in Exhibit 6.

DOR will be estimated in the all treated population using the Kaplan-Meier (KM) product limit method and displayed graphically. The KM estimate of the median DOR and the corresponding two-sided 95% CI, calculated using the Brookmeyer and Crowley's method (log-log transformation), will be presented.

Time to response, defined as the time from first dose date to the date of first confirmed response (CR or PR), will also be estimated in the all treated population using the Kaplan-Meier (KM) product limit method. The KM estimate of the median time to response and the corresponding two-sided 95% CI, calculated using the Brookmeyer and Crowley's method (log-log transformation), will be presented alongside DOR.

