10.1. Estimand framework

A summary of the attributes of the primary estimand is provided in Table 1.

Table 1. Estimand attributes for the primary efficacy analysis

Estimand attribute	Description of attribute
Target population	All treated population: All patients treated with CDX-3379.
Primary patient-level variable	Best overall response (BOR) according to RECIST 1.1. Patients can have a BOR of complete response (CR), partial response (PR), stable disease (SD), progressive disease (PD), or unknown.
Handling of intercurrent events	Alternative anti-cancer therapies will be intercurrent events in the determination of BOR. Assessments that occur after the date of documented progression per RECIST 1.1. or the date of anti-cancer treatment, whichever occurs first, will not contribute to the determination of BOR.
Population-level summary	ORR, defined as the percentage of patients who achieve a best response of CR or PR, confirmed according to RECIST 1.1., for all patients treated with CDX-3379 in combination with cetuximab.

The trial product estimand is defined as ORR based on assessments on or prior to the date of PD or data of anti-cancer therapy, whichever occurs first. Patients who discontinue study therapy for reasons other than progression will continue to have tumor assessments until disease progression or initiation of subsequent anti-cancer therapy, whichever occurs first. Therefore, treatment discontinuation is not considered an intercurrent event. The primary efficacy analysis will be an estimation analysis for this estimand (point estimate of ORR and associated 95% confidence interval).

Duration of response is an important secondary analysis because it characterizes ORR. A summary of the attributes of the estimand associated with this important secondary endpoint is provided in Table 2.

Table 2. Estimand attributes for the important secondary efficacy analysis

Estimand attribute	Description of attribute
Target population	All patients treated with CDX-3379 who have a BOR of confirmed CR or PR (objective response).

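### SAP 6.2.1 plans an all-treated Kaplan-Meier median for time to response with no rule for patients who never respond, so the median cannot describe when responders respond

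*SAP*

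**What the plan says.** SAP 6.2.1 adds time to response in the last paragraph of the duration-of-response section. It "will also be estimated in the all treated population using the Kaplan-Meier (KM) product limit method", and "The KM estimate of the median time to response and the corresponding two-sided 95% CI", by the Brookmeyer-Crowley method, are to appear next to duration of response (DOR).

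Four other places bear on this:

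- **Censoring.** SAP 4.10 refers the reader to Section 6. The only table there, Exhibit 6, counts progression and death as events. That suits PFS and DOR and cannot be applied to time to response. No competing-risk method is named.
- **When response can be observed.** SAP 6 ends tumour assessments at progression or new anti-cancer therapy, and SAP 6.1 closes best response at the earlier of the two. A patient who progresses first can no longer be counted as a responder.
- **DOR population.** The estimand table for DOR (SAP 10.1, Table 2) limits it to "All patients treated with CDX-3379 who have a BOR of confirmed CR or PR (objective response"), whereas the 6.2.1 text says all treated for DOR as well. Time to response has no estimand table.
- **Protocol.** Time to response is not among the endpoints in Protocol 12.2.

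**The concern.** Kaplan-Meier treats a censored patient as someone who could still have the event later. Here progression and death end the chance of response, so they are competing events. The SAP does not say what happens to such patients, and each of the two obvious choices gives a poor summary. Holding them at risk gives a median that needs more than half of all treated patients to respond. Censoring them at progression or death passes their share of risk to those who remain and raises the estimated response probability above the truth.

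At stake is one descriptive figure. Printed beside DOR, a time-to-response median would be read as the typical wait among responders, which it would not be.

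**Working it through.** **Inputs from the documents.** About 45 treated patients, at least 15 of them FAT1-positive (SAP 4.9); true ORRs of 20%, 30%, 40% and 50% (Protocol Table 11); scans about every 6 weeks (SAP 6); two-sided 95% CIs (SAP 4.2).

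**The plan's own figures reproduce.** No figure is stated for time to response, so the check is on sample size. The exact binomial P(X ≥ 15 | 45, 0.40) is 85.7%, against ">80% power to rule out <20% ORR based on the lower 95% confidence bound" and 86% in Table 11. P(X ≥ 5 | 15, 0.40) is 78.3%, against nearly 80% in SAP 4.9 and 78% in Table 11.

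**Rule A: non-responders stay at risk to the end of follow-up.** The curve ends at the observed ORR, so nothing is overstated. The median exists only if at least half respond: 22/45 = 48.9% is too few and 23/45 = 51.1% is enough. For 15 patients the requirement is 8.

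| True ORR | P(X ≥ 23 of 45) | P(X ≥ 8 of 15) |
|---|---|---|
| 20% | <0.001% | 0.4% |
| 30% | 0.24% | 5.0% |
| 40% | 8.6% | 21.3% |
| 50% | 50% | 50% |

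**Rule B: non-responders are censored at progression or death.** This needs assumptions that the documents do not supply: 60%, 30% and 10% of responders first respond at weeks 6, 12 and 18; non-responders leave at scans; and their median PFS is 6 to 16 weeks. The proportion of non-responders remaining after each 6-week interval is then 0.5^(6/6) = 0.50 to 0.5^(6/16) = 0.77.

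Expected counts at ORR 20% with a 6-week median PFS (9 responders, 36 non-responders):

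- Week 6: 45 at risk, 5.4 respond, S = 1 − 5.4/45 = 0.88. Then 18 are censored.
- Week 12: 45 − 5.4 − 18 = 21.6 at risk, 2.7 respond, S = 0.88 × (1 − 2.7/21.6) = 0.77. Then 9 are censored.
- Week 18: 21.6 − 2.7 − 9 = 9.9 at risk, 0.9 respond, S = 0.77 × (1 − 0.9/9.9) = 0.70.

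So 1 − S = 30%, although 9/45 = 20% respond. Simulation under the same assumptions gives these ranges, for non-responder median PFS of 6 to 16 weeks:

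| True ORR | Week-18 1 − KM | Trials reaching a median (approx.) |
|---|---|---|
| 20% | 30% to 23% | 3% to 0% |
| 30% | 44% to 34% | 27% to 2% |
| 40% | 56% to 45% | 70% to 27% |
| 50% | 67% to 55% | 96% to 74% |

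At ORR 40%, at least 23 patients respond in only 8.6% of trials. The share of reached medians backed by a true majority of responders is therefore about 8.6/70 = 12% to 8.6/27 = 32%. At ORR 30% it is about 0.24/27 = 1% to 0.24/2 = 12%. The remainder come from the censoring.

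**What the median would say.** In the same model at ORR 40% with a 6-week median PFS, expected S is 0.76 at week 6, 0.56 at week 12 and 0.44 at week 18. The all-treated median is 18 weeks. Among responders, 60% have responded by week 6, so their median is 6 weeks.

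**Sensitivity.** A second set of assumptions puts responses at scans 1 to 4 in shares 60/25/10/5%, with a 0.3, 0.5 or 0.7 chance per interval that a non-responder progresses or dies. The final 1 − KM averages 25/35/56% at ORR 20%, 37/49/71% at 30% and 49/62/82% at 40%. The direction is the same and the size depends strongly on how fast non-responders progress.

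**The case against.** A reader might infer that the median will usually not be estimable and also that the estimate overstates response. The documents do not support that pair as a general statement. Each consequence depends on a censoring rule that the SAP does not write down, and the two mostly do not occur together. Under Rule A nothing is overstated. Under Rule B a median appears in about 70% to 27% of simulated trials at ORR 40% and in 96% to 74% at 50%. The 50% column of Protocol Table 11 also matters: at that rate a genuine median occurs in half of trials even under Rule A. All of this stands.

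Three further points can be made for the plan:

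- It specifies no time-to-response graph, only a median and CI. ORR is reported directly with an exact CI, and a swimmer plot shows individual responses. This stands, so the overstatement would reach readers only through the median.
- All treated may be loose wording, since 6.2.1 uses the same phrase for DOR, which Table 2 limits to responders. This is plausible, but no table makes that correction for time to response. Because this endpoint starts at first dose, the analysis can be run literally on every treated patient, and a programmer may do so.
- The endpoint is not in the protocol and supports no hypothesis test. This stands and sets the severity.

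**Conclusion.** The defect holds: the stated method is incomplete, and under neither completion does its median describe when responders respond. With non-responders kept at risk, the median is almost never reached at ORR 20% to 30%, is reached in about 9% of trials at 40%, and in half at 50%. These are exact binomial results and need no outside assumption. With censoring at progression or death, the Kaplan-Meier response probability is too high, by roughly 3 to 10 percentage points at ORR 20%, 4 to 14 at 30% and 5 to 16 at 40%. A median reached at an ORR below 50% is then usually an artefact. Those sizes rest on the assumed response timing and PFS range. Censoring at progression or death is the likelier default because assessments stop there, but that is an inference and the SAP does not say it.

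Severity is minor. The primary ORR, the sample size and the other secondary endpoints are unaffected. SAP 6.3 repeats the secondary analyses by subgroup with the 6.2 methods. Its detailed list omits time to response, so a carry-over to the FAT1-positive patients is possible but not stated.

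**What to change.** In SAP 6.2.1, delete the all-treated Kaplan-Meier median and CI for time to response. Summarise time to response in confirmed responders by number, median, quartiles and range. This also puts it in the same population as the DOR estimand in Table 2.

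If an all-treated estimate is wanted, use the cumulative incidence of confirmed response with progression or death as a competing event, and state how new anti-cancer therapy before response is handled. With complete follow-up that curve ends at the observed ORR.

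While editing 6.2.1, align its all-treated wording for DOR with Table 2. The cost is a sentence or two in the SAP and a simpler table, with no new data and no protocol amendment.

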6.2.2. Clinical benefit response

CBR, defined as the percentage of patients who achieve a best response of confirmed CR or PR, or SD for at least 12 weeks. Best response is assessed as described for ORR.

CBR will be calculated in the all treated population as defined above, and the corresponding two-sided 95% exact CI will be calculated using the Clopper-Pearson method.

6.2.3. Disease control rate

Disease control rate (DCR), defined as the percentage of patients who achieve a best response of confirmed CR or PR, or SD. Best response is assessed as described for ORR.

DCR will be calculated in the all treated population as defined above, and the corresponding two-sided 95% exact CI will be calculated using the Clopper-Pearson method.

6.2.4. Progression-free survival

PFS is defined as the time from the start of study treatment to the time of progression or death, whichever occurs first. Patients who have not progressed or died will be censored on the date of last evaluable tumor assessment; patients who did not have any on-study assessments and did not die will be censored on the date of first dose. If a patient receives subsequent anti-cancer treatment before documented progression, then PFS will be censored on the last evaluable tumor assessment on or before initiation of subsequent anti-cancer treatment. The censoring rules are outlined in Exhibit 6.

Exhibit 6. Censoring rules

Situation	Date of Event or Censoring	Outcome
Progression	Date of progression	Event
Death without progression	Date of death	Event
No baseline disease assessment	Date of first dose	Censored
No on-study disease assessments and no death	Date of first dose	Censored
No progression and no death	Date of last evaluable tumor assessment	Censored
Subsequent anti-cancer therapy before documented progression	Date of last evaluable tumor assessment on or before initiation of subsequent anti-cancer therapy	Censored

PFS will be estimated in the all treated population using the KM product limit method and displayed graphically. The KM estimate of the median PFS and the corresponding two-sided 95% CI, calculated using the Brookmeyer and Crowley's method (log-log transformation), will be presented.

The number and percentage of patients with an event and the type of event (progression or death) will be summarized. The status of patients who are censored in the PFS KM analysis will be presented using the following categories:

- No baseline or inadequate baseline assessment
- No post-baseline or death before first scheduled assessment
- Received additional anti-cancer therapy
- Death or progression after ≥ 2 missed assessments
- Alive and without disease progression

The KM estimates of the median PFS rate at 3 months and 6 months will be presented with the corresponding 95% CIs.

6.2.4.1. Subsequent therapy

The number and percentage of patients receiving subsequent cancer therapies will be summarized by the type of therapy as reported on the eCRF (radiotherapy, cancer medication, other anti-cancer treatment, biopsy, resection, or other surgery). Biopsies will not be considered for censoring purposes.

A by-patient listing of subsequent therapy will be produced for patients who had any subsequent therapy.

6.2.5. Overall survival

OS is defined as the time from the start of study treatment to the time of death. Patients who have not died will be censored on the last known alive date.

OS will be estimated in the all treated population using the KM product limit method and displayed graphically. The KM estimate of the median OS and the corresponding two-sided 95% CI, calculated using the Brookmeyer and Crowley's method (log-log transformation), will be presented.

The number and percentage of patients with an event will be summarized. The status of patients who are censored in the OS KM analysis will be presented using the following categories:

- Alive
- Lost to follow-up
- Withdrawal of consent
- Study closure

The KM estimates of the median OS rate 6 months, 9 months, 12 months, and 18 months will be presented with the corresponding 95% CIs.

6.3. Subgroup analyses

The primary and secondary efficacy analyses will be repeated for each of the following subgroups using the methods described in Sections 6.1 and 6.2:

- FAT1 mutation status (positive vs. negative) among treated subjects who have evaluable FAT1 results
- FAT1/NOTCH mutation status (positive for either FAT1 or NOTCH vs. negative for both) among treated subjects who have evaluable FAT1 and NOTCH results
- Primary tumor site (oral cavity vs. other) in all treated subjects

Specifically, the number and percentage of patients in each category of BOR will be summarized for each subgroup. The estimates of ORR, CBR, and DCR and the corresponding two-sided 95% exact CIs for each subgroup will be presented in forest plots for each endpoint.

DOR, PFS, and OS will be estimated in each subgroup using the KM product limit method and displayed graphically with the estimated median and two-sided 95% CI. The median estimates for each subgroup will also be presented in forest plots.

6.4. Handling of dropouts or missing data for the primary and secondary analyses

No imputations will be made for missing values. Summaries will be based on observed data only.

6.5. Interim analyses and data monitoring

There are no planned interim analyses for this study.

6.6. Multiplicity

No adjustments for multiplicity will be made in this study.

7. Safety summaries

All safety analyses will be based on the all treated population.

7.1. Extent of exposure

Study drug exposure will be summarized for the all treated population. Summaries will be separated for CDX-3379 and cetuximab. Summaries will include the number of infusions per patient as well as cumulative dose received, relative dose intensity, and duration of treatment. These parameters are defined in Exhibit 7.

Exhibit 7. Study drug parameter definitions

	CDX-3379	Cetuximab
Dosing schedule per protocol	12 mg/kg every 3 weeks, with option to increase to 15 mg/kg	400 mg/m ² IV (loading dose) once, then 250 mg/m ² weekly
Dose	Dose (mg/kg) is defined as total dose administered (mg)/most recent weight (kg).	Dose (mg/m ²) is defined as total dose administered (mg)/most recent body surface area (BSA) (m ²).
Cumulative dose	Cumulative dose (mg/kg) is the sum of the doses administered to a patient.	Cumulative dose (mg/m ²) is the sum of the doses administered to a patient.
Dose intensity ^a	Cumulative dose / [(Last dose date - first dose date + 21)/7]	Cumulative dose - first dose / [(Last dose date - second dose date + 7)/7]
Relative dose intensity (%) ^b	(Dose intensity/4 mg/kg/wk)*100	(Dose intensity/250 mg/m ² /wk)*100
Duration of treatment (weeks)	(Last dose date - First dose date)/7	(Last dose date - First dose date)/7

a. Dose intensity reported in mg/kg/wk for CDX-3379 and mg/m²/week for cetuximab. Dose intensity for cetuximab starts at the second dose.

b. Relative dose intensity for cetuximab starts at the second dose.

Dose delays will be summarized as the number of patients with at least one delay, the number of doses delayed per patient, and the reason for the delay. [REDACTED]

[REDACTED]

[REDACTED]

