2.3. Study treatments

Patients will be treated with CDX-3379 plus cetuximab until progressive disease, unacceptable toxicity, or other criteria for discontinuation of study treatment.

A cycle is defined as 21 days. The dose of CDX-3379 is 12 mg/kg, with the option to increase the dose to 15 mg/kg if tolerated, delivered via intravenous (IV) infusion over 60 minutes. CDX-3379 will be administered every 3 weeks (on Day 1 of each 21-day cycle).

Cetuximab will be dosed with an initial loading dose of 400 mg/m² on Day 1 over 2 hours, followed by weekly doses of 250 mg/m² over 60 minutes. Patients who were previously treated with cetuximab within three months of study enrollment and required dose reduction due to adverse events attributed solely to cetuximab (e.g., rash) may initiate cetuximab at the same dose as was last received in the prior regimen, with or without an initial loading dose, as clinically appropriate. Cetuximab will be administered on Days 1, 8, and 15 of each 21-day

CELLDEX CDX3379-04: STATISTICAL ANALYSIS PLAN

[figure not shown]
June 24, 2020

Page 4

[figure not shown]
cycle. On Day 1 of each cycle, cetuximab should be administered approximately one hour after the completion of CDX-3379 infusions (and after completion of PK sampling).

As a routine precaution, the investigative site's medical staff is to closely observe patients for the duration of the cetuximab and CDX-3379 infusions and for at least one hour after the end of the infusions.

Exhibit 1. Study schema

* If CDX-3379 is discontinued, the patient is considered to be discontinued from the study treatment.

CONFIDENTIAL

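### The cetuximab dose-intensity formula in SAP Exhibit 7 lacks parentheses around its numerator, so read literally it returns almost the cumulative dose instead of a weekly rate

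*SAP*

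**What the plan says.** SAP section 7.1 plans separate exposure summaries for CDX-3379 and cetuximab in everyone treated with CDX-3379. They cover infusions per patient, cumulative dose, relative dose intensity and treatment duration, and Exhibit 7 supplies the definitions.

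For cetuximab, Exhibit 7 gives:

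- schedule: "400 mg/m ² IV (loading dose) once, then 250 mg/m ² weekly"
- dose intensity: "Cumulative dose - first dose / [(Last dose date - second dose date + 7)/7", then a closing square bracket
- relative dose intensity: dose intensity as a percentage of a 250 mg/m²/wk reference ("Dose intensity/250 mg/m ² /wk)*100")

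Note a fixes the units: "Dose intensity reported in mg/kg/wk for CDX-3379 and mg/m²/week for cetuximab". Notes a and b both set the starting point; in the words of note b, "Relative dose intensity for cetuximab starts at the second dose".

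The CDX-3379 column divides its whole numerator by weeks, "Cumulative dose / [(Last dose date - first dose date + 21)/7", again with a closing bracket, and uses a 4 mg/kg/wk reference.

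SAP section 2.3 allows certain patients with a recent cetuximab dose reduction to start "with or without an initial loading dose, as clinically appropriate".

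Protocol section 12.5.6 lists only duration, number of doses, total dose and reasons for modification. Exhibit 7 is therefore the only definition of dose intensity in the documents.

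**The concern.** Division binds before subtraction. The printed cetuximab expression therefore divides the first dose by weeks and subtracts that from the cumulative dose. It takes a quantity in mg/m² per week away from one in mg/m², and the result grows with every dose given. That cannot be the rate required by note a, and it cannot sensibly be compared with 250 mg/m²/wk in the next row.

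An output would be programmed from this formula. If it is coded as printed, most patients on continuing treatment would show a relative dose intensity of several hundred percent or more, and the table would say nothing about how much of the planned cetuximab was delivered alongside CDX-3379.

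A smaller gap lies beside it. The formula needs a second dose date, and Exhibit 7 does not say what to report for a patient who received only one cetuximab dose.

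**Working it through.** **Inputs, all from Exhibit 7.** First dose F = 400 mg/m², later doses 250 mg/m² weekly, reference 250 mg/m²/wk. Assume full doses exactly on schedule. For n doses:

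- cumulative dose C = 400 + 250(n − 1)
- weeks W = (last dose date − second dose date + 7)/7 = n − 1

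**The plan's own figure.** A patient exactly on this schedule should return the reference, 250 mg/m²/wk or 100%.

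**Two readings.** As printed: C − F/W. With the numerator enclosed: (C − F)/W.

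| Doses | C | W | As printed | Relative | Enclosed | Relative |
|---|---|---|---|---|---|---|
| 2 | 650 | 1 | 650 − 400/1 = 250 | 100% | 250/1 = 250 | 100% |
| 3 | 900 | 2 | 900 − 400/2 = 700 | 280% | 500/2 = 250 | 100% |
| 6 | 1650 | 5 | 1650 − 400/5 = 1570 | 628% | 1250/5 = 250 | 100% |
| 9 | 2400 | 8 | 2400 − 400/8 = 2350 | 940% | 2000/8 = 250 | 100% |
| 10 | 2650 | 9 | 2650 − 400/9 = 2605.6 | 1042% | 2250/9 = 250 | 100% |
| 12 | 3150 | 11 | 3150 − 400/11 = 3113.6 | 1245% | 2750/11 = 250 | 100% |

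The printed formula matches the reference only at two doses, where W = 1 and the two readings coincide. The enclosed formula returns it at every n of 2 or more.

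**Check on the other column.** With n on-time CDX-3379 doses of 12 mg/kg every 21 days, intensity is 12n / [(21(n − 1) + 21)/7] = 12n/3n = 4 mg/kg/wk, which is that column's own reference. The fault is confined to cetuximab.

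**One cetuximab dose.** There is no second dose date, so W is undefined under either reading.

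**No loading dose (illustrative patients, 6 doses of 250 mg/m² weekly).** C = 1500.

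- Enclosed: (1500 − 250)/5 = 250, or 100%.
- Counting all doses from the first: 1500/6 = 250, or 100%. The results are identical.
- If dose 2 comes two weeks late, the enclosed formula still gives 1250/5 = 250 (100%). Counting from the first dose gives 1500/8 = 187.5 (75%).

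The last difference comes from leaving out the first interval. The convention does the same for patients who receive a loading dose.

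**The case against.** The strongest reply is that nobody would misread the exhibit. Note a gives a weekly unit, both notes say the calculation starts at the second dose, the next row divides by a weekly reference, and the CDX-3379 column shows the intended structure. A programmer who saw 1245% would look again. That reply stands as far as it goes: the intent is recoverable and the method is sound. It does not make the printed expression correct, and the SAP Introduction gives the SAP precedence over the protocol, so the formula should be right as written.

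Three stronger readings are tempting, and the documents do not support them.

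- A reader might infer a tenfold error for everyone with several doses. The error is nil at 2 doses, 2.8-fold at 3 and about 6-fold at 6. It reaches tenfold only at 10 on-schedule doses.
- A reader might infer that the formula breaks down for patients who start without a loading dose. Once the numerator is enclosed it gives a valid value for them, equal to the all-doses value on a constant weekly dose. Dropping the first dose for everyone is a stated convention. A separate formula for these patients would count the first interval in one group and not in the other, so a late second dose would lower intensity in one group only.
- A reader might infer that losing one-dose patients seriously distorts the picture of exposure. The documents give no basis for the number of such patients, and a single dose could reflect early progression as well as intolerance. These patients remain in the summaries of infusions, cumulative dose and duration, and SAP section 4.2 provides by-patient listings. Text after the dose-delay sentence in section 7.1 is also redacted, so a rule for them may exist there.

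**Conclusion.** The point holds as a formula error with a clear intended meaning. Taken literally, the printed expression overstates cetuximab relative dose intensity from the third dose onward, and by more with each further dose: 280% at 3, 628% at 6 and 1245% at 12, where 100% is meant. These sizes assume full doses on the exhibit's 400-then-250 weekly schedule; delays or reductions would change the figures but not the fault.

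The missing rule for patients with fewer than two cetuximab doses is a matter of detail, judged on the visible text only. Only the descriptive exposure summary is affected. Response rate, duration of response, progression-free survival and overall survival do not use this quantity.

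**What to change.** In Exhibit 7, enclose the cetuximab numerator: (cumulative dose − first dose), all divided by the weeks term already printed. Keep the start-at-second-dose convention for all patients, with or without a loading dose.

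As a minor addition, add a note that cetuximab dose intensity and relative dose intensity are not calculable for patients with fewer than two cetuximab doses, and show the number of such patients in the table.

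The cost is one pair of parentheses and one footnote. SAP section 4.11 already provides the route, a revised plan before database lock. No new data are needed and no other analysis changes.

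### Cetuximab dose intensity runs from the second dose actually given, so a delay between the first two doses is left out of relative dose intensity

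*SAP*

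**What the plan says.** SAP Section 2.3 plans a cetuximab loading dose of 400 mg/m² on Day 1, "followed by weekly doses of 250 mg/m² over 60 minutes". It also states: "Cetuximab will be administered on Days 1, 8, and 15 of each 21-day" cycle. The second dose is therefore due on Day 8.

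Exhibit 7 in SAP Section 7.1 gives cetuximab dose intensity as "Cumulative dose - first dose / [(Last dose date - second dose date + 7)/7" (closing bracket omitted here). Note a says "Dose intensity for cetuximab starts at the second dose", and note b says "Relative dose intensity for cetuximab starts at the second dose". Relative dose intensity divides the result by 250 mg/m²/week ("Dose intensity/250 mg/m"²/wk). Cumulative dose is the sum of doses administered, and no planned-date anchor is given, so the second dose date is the date that dose was given.

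For CDX-3379 the same exhibit uses "Cumulative dose / [(Last dose date - first dose date + 21)/7", which starts at the first dose.

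Section 7.1 also summarizes dose delays, as patients with a delay, doses delayed per patient and reasons. Duration of treatment is measured from the first dose.

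**The concern.** Leaving the loading dose out of the numerator is reasonable, because 400 mg/m² is not part of the 250 mg/m² weekly rate. The clock should then start when the weekly phase is due to begin. Exhibit 7 starts it when that phase did begin. Time lost between doses 1 and 2 is removed from the denominator, and the doses missed in that time never enter the numerator. A hold of the same length one interval later is counted in full. Two patients who receive the same drug over the same calendar time can therefore report different relative dose intensities, and the patient held earlier gets the better figure.

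What is at stake is how far relative dose intensity can be read as the share of planned weekly cetuximab that was delivered.

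**Working it through.** **Inputs.** Schedule of 400 then 250 mg/m² weekly, second dose due Day 8 (SAP 2.3 and Exhibit 7); reference 250 mg/m²/week = 100% (Exhibit 7); visit window ±1 day on Day 8 (SAP Exhibit 4).

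**Formulas.**
- SAP, brackets supplied: (cumulative − first dose) / [(last − second dose date + 7)/7].
- Due-date clock: the second dose date is replaced by first dose date + 7. The denominator becomes (last − first − 7 + 7)/7 = (last − first)/7.

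**1. Reproduce the 100% reference.** Doses on Days 1, 8, 15, 22, 29, 36 total 400 + 5 × 250 = 1650. SAP: (1650 − 400)/[(36 − 8 + 7)/7] = 1250/5 = 250, or 100%. Due-date clock: 1250/[(36 − 1)/7] = 1250/5 = 250, or 100%. Read literally without the brackets, the SAP formula gives 1650 − 400/5 = 1570, or 628%, so the bracketed reading must be the intended one.

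**2. Two weekly doses held before the second dose.** Doses on Days 1, 22, 29, 36; numerator 3 × 250 = 750.
- SAP: 750/[(36 − 22 + 7)/7] = 750/3 = 250, or 100%.
- Due-date clock: 750/[(36 − 1)/7] = 750/5 = 150, or 60%.

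**3. Two weekly doses held after the second dose.** Doses on Days 1, 8, 29, 36; numerator 750.
- SAP: 750/[(36 − 8 + 7)/7] = 750/5 = 150, or 60%.
- Due-date clock: also 60%.

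**4. General case.** Take k doses in total, the second d weeks late, and full weekly dosing afterwards. The SAP gives 250(k − 1)/(k − 1) = 250, always 100%. The due-date clock gives (k − 1)/(k − 1 + d):

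| Total doses | 1 week late | 2 weeks late | 3 weeks late |
|---|---|---|---|
| 2 | 50% | 33% | 25% |
| 6 | 83% | 71% | 63% |
| 12 | 92% | 85% | 79% |
| 18 | 94% | 89% | 85% |

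**5. Early delay plus dose reduction.** Doses on Days 1, 22, 29, 36, with 200 mg/m² from the second dose as an illustrative value: SAP 600/3 = 200, or 80%; due-date clock 600/5 = 120, or 48%. The reduction is counted under the SAP rule; the delay is not.

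**6. Side effect of the due-date clock.** For a two-dose patient with the second dose in window, Day 7 gives 250/(6/7) = 292, or 117%, and Day 9 gives 250/(8/7) = 219, or 87.5%. The SAP rule gives 100% for both. With only one dose, the due-date clock gives 0/0, and the SAP rule has no second dose date to use.

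**The case against.** The strongest defence is that the convention is disclosed. Both notes say the measure starts at the second dose, and intensity over the weekly phase is a recognizable quantity. That stands as a description of intent, but disclosure does not make the figure consistent: cases 2 and 3 still differ for the same drug over the same time.

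The second defence is that the delay is reported elsewhere, in the delay counts with reasons and in duration of treatment. This largely stands. A reader might infer that an early delay disappears from the safety report, and the documents do not support that. What the visible text lacks is a summary of the length of delay. Text after the delay sentence is redacted, so nothing can be concluded about further summaries there.

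Three other stronger readings also fail:
- That any patient with an early hold reads 100%. This is true only when the hold falls between doses 1 and 2 and later dosing is full and weekly. Holds after the second dose and dose reductions still count.
- That the different starting points spoil a comparison of the two drugs. The exposure summaries are separate and no such comparison is planned.
- That early tolerability will be misreported overall. Delays can arise from holidays or weather (SAP Exhibit 4, note 1), so relative dose intensity is not a clean measure of tolerability in any case, and delays are tabulated with their reasons.

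**Conclusion.** The point holds, at minor severity. With the brackets supplied, Exhibit 7 leaves any delay between the first and second cetuximab dose out of relative dose intensity, while the same hold later is counted. In the worked example the reported figure is 100% instead of 60%. The gap is largest in short courses and narrows with longer ones: a two-week delay costs 67 percentage points with 2 doses, 29 with 6 and 11 with 18.

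These figures assume 400 then 250 mg/m² and full weekly dosing after the delay. SAP 2.3 lets some previously treated patients start at an earlier reduced dose, with or without loading, so the examples do not describe everyone. The documents do not say how many patients will have such a delay, and those exactly on schedule are unaffected. Only this descriptive exposure measure is involved; the response rate and the other efficacy analyses do not use it.

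**What to change.** In Exhibit 7, define cetuximab dose intensity as (cumulative dose − first dose) / [(last dose date − first dose date)/7]. This also supplies the missing brackets. Change notes a and b to say that the measure starts 7 days after the first dose. State that it is not calculated for patients with only one cetuximab dose.

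The cost is one formula, two amended notes and one added sentence, with no new data and no change to any dosing rule. Reported relative dose intensity will be somewhat lower where the second dose was late. A second dose within its ±1 day window will also move the value in very short courses (117% or 87.5% in the two-dose cases above), and a table footnote should say so.
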